## 4 Trial Design

### 4.1 Type/Design of Trial

This is a Japanese, multicenter, open-label, uncontrolled, phase 3 long-term trial to assess the safety and efficacy of ETC-1002 long-term administration in patients with hyper-LDL cholesterolemia who are being treated for hyper-LDL cholesterolemia but have inadequate control and cannot achieve the lipid management goals. The trial population will include patients with an inadequate response to statins who cannot achieve the lipid management goals despite statin therapy, and patients who are determined to have difficulty in treatment with statins and cannot achieve the lipid management goals. Patients with difficulty in treatment with statins are defined as those who cannot achieve the lipid management goals for the following reasons: patients who have experienced safety problems caused by statin administration which resolved after discontinuation or dose reduction, or patients who have a history of statin administration and are judged to have concerns of safety problems associated with the administration or dose increase of

statins. In addition, subjects who have completed the treatment period in the phase 3 confirmatory trial (Protocol No. 346-102-00002) can also be enrolled in this trial, as they are in the same population and their enrollment allows assessments of the occurrence of AEs over a longer period.

A schematic of the trial design is presented in Figure 1.2-1.

This trial consists of the screening period, the treatment period, and the follow-up period.

Subjects who are judged to be eligible at screening will proceed to the treatment period.

Subjects proceeding to the treatment period who have been receiving treatment using lipid-lowering drugs since before informed consent should continue the treatment without changing the type or dose and regimen in addition to being orally administered ETC-1002 at 180 mg once daily for 52 weeks.

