  - Aspartate aminotransferase (AST) or alanine aminotransferase (ALT) of  $\geq 3 \times$  ULN or total bilirubin of  $\geq 2 \times$  ULN at screening (Week -2)
- 10) Patients with a history or current chronic musculoskeletal symptoms that may be difficult to differentiate from myalgia (eg, fibromyalgia)
- 11) Patients with CK of  $> 3 \times$  ULN at screening (Week -2)
- 12) Patients with a history or current renal dysfunction, nephritic syndrome, or nephritis and with estimated glomerular filtration rate (eGFR) of  $\leq 30$  mL/min/1.73 m^2 at screening (Week -2)
- 13) Patients who have had gastrointestinal surgery that may affect drug absorption (eg, Lap-Band® or gastric bypass)
- 14) Patients who have undergone surgery, chemotherapy, or radiation therapy for active malignancy (excluding properly treated nonmetastatic basal or squamous cell carcinoma of the skin and cervical carcinoma in situ) within the past 5 years prior to screening (Week -2)
- 15) Patients with a history of drug, alcohol, or cocaine abuse within the past 2 years prior to screening (Week -2)
- 16) Patients who have had blood collection (eg, blood donation) in a cumulative amount exceeding 200 mL within 4 weeks, 400 mL within 12 weeks, or 1200 mL within 1 year prior to screening (Week -2)

- 17) Patients who have used any investigational drug not approved in Japan within either 4 weeks or 5 times the half-life of the drug, whichever is longer, prior to screening (Week -2)
- 18) Patients who took the IMP in Trial 346-102-00001 or patients who have used ETC-1002 in the past
- 19) Patients who used or received the following drugs (including food) or therapies within the specified period, or who are planning to use or receive them by the end of the tests at Week 52

	Drugs (including food) or therapies	Prohibited period
1.	Systemic corticosteroids	From 3 months prior to Week -2 to the end of the tests at Week 52 (or to the completion of the assessments at Discontinuation Visit, if applicable) However, if the drug has been used with the same dose and regimen since 3 months prior to Week -2, it may be used concomitantly with no change in dose until the end of the tests at Week 52 (or to the completion of the assessments at Discontinuation Visit, if applicable)
2.	Lomitapide	From 3 months prior to Week -2 to the end of the tests at Week 52 (or to the completion of the assessments at Discontinuation Visit, if applicable)

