4.	Red yeast rice and food containing red yeast rice	From Day 1 to the end of the tests at Week 52 (or to the completion of the assessments at Discontinuation Visit, if applicable)
5.	LDL apheresis	From Day 1 to the end of the tests at Week 52 (or to the completion of the assessments at Discontinuation Visit, if applicable)

- 9) Patients in whom the following drugs (therapies) are changed prior to Day 1 or in whom initiation of the following drugs (therapies) is planned by the end of the tests at Week 52

	Drugs or therapies	Period in which the drug or therapy cannot be changed or newly started
1.	Female or male hormone replacement	From 6 weeks prior to Day 1 to the end of the tests at Week 52 (or to the completion of the assessments at Discontinuation Visit, if applicable)
2.	Thyroid replacement	From 6 weeks prior to Day 1 to the end of the tests at Week 52 (or to the completion of the assessments at Discontinuation Visit, if applicable)
3.	Diabetes medications	From 4 weeks prior to Day 1 to the end of the tests at Week 52 (or to the completion of the assessments at Discontinuation Visit, if applicable)
4.	Obesity medications	From 3 months prior to Day 1 to the end of the tests at Week 52 (or to the completion of the assessments at Discontinuation Visit, if applicable)

- 10) Patients otherwise judged inappropriate for participating in the trial in the opinion of the investigator or subinvestigator

A definition of childbearing potential can be found in [Section 10.3](#).

Subjects must agree to the restrictions on medications and lifestyle described in [Section 6.5.1](#) and [Section 5.3](#), respectively.

[Rationale for the exclusion criteria]

- Newly Enrolled Subjects
  - 1) to 2) These criteria are set in consideration of safety, because the safety of administration of ETC-1002 during pregnancy and breast-feeding has not been established.
  - 3) to 9), 12), 15), 21) These criteria are set in consideration of the safety of the subjects.
  - 10) to 11), 14), 18) These criteria are set to appropriately evaluate the safety of ETC-1002.
  - 13) This criterion is set to avoid the influence of such a surgery on ETC-1002 absorption, etc.
  - 16) This criterion is set according to the Blood Sampling Criteria of the New Blood Program Advisory Committee to ensure the safety of the subjects.
  - 17), 19) to 20) These criteria are set to appropriately evaluate the efficacy and safety of ETC-1002.

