### **8.8 Adverse Events**

#### **8.8.1 Definitions**

An AE is defined as any untoward medical occurrence in a clinical trial subject administered a trial intervention\*, and does not necessarily have a causal relationship with

\* Refer to the guidance in Article 2 of the revised GCP. No trial interventions other than the IMP will be used in this clinical trial.

this treatment. In this trial, any untoward medical occurrence in a subject not receiving the trial intervention will be included. Adverse events would not include information recorded as medical history at screening for pre-planned procedures for which the underlying condition was known and no worsening occurred. In addition, if an AE that developed in a rollover subject during the phase 3 confirmatory trial (Protocol No. 346-102-00002) continues without recovery/resolution but does not worsen, the event will not be included as an AE in this trial. An adverse reaction is any untoward and unintended response to a trial intervention related to any dose administered.

A suspected adverse reaction is any AE for which there is a reasonable possibility that the trial intervention caused the AE.

Treatment-emergent AEs (TEAEs) are defined as AEs with an onset date on or after the start of IMP treatment. In more detail, TEAEs are all AEs which started after the start of IMP treatment; or if the event was continuous from baseline and worsened after the start of IMP treatment.

An SAE includes any event that results in any of the following outcomes:

- Death
- Life-threatening; ie, the subject was, in the opinion of the investigator or subinvestigator, at immediate risk of death from the event as it occurred. It does not include an event that, had it occurred in a more severe form, might have caused death.
- Persistent or significant incapacity/disability or substantial disruption of the ability to conduct normal life functions.
- Requires inpatient hospitalization or prolongs hospitalization.
  - Hospitalization itself should not be reported as an SAE; whenever possible, the reason for hospitalization should be reported.
  - Hospitalizations or prolonged hospitalizations for social admissions (ie, those required for reasons of convenience or other nonmedical need) are not considered SAEs.
  - Prescheduled hospitalization to address a condition that has existed prior to the signing of the ICF should not be considered an SAE.
- Congenital anomaly/birth defect.

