### 8.8.2 Eliciting and Reporting Adverse Events

The investigator or subinvestigator will regularly assess the subjects for the occurrence of AEs. To avoid bias in eliciting AEs, subjects should be asked the nonleading question: “How have you felt since your last visit?” All AEs (serious and nonserious) reported by the subject must be recorded on the source documents and eCRF provided by the sponsor. Adverse event collection will begin after a subject signs the ICF and will continue until the end of the follow-up period. All AEs must be recorded in the eCRF after subject informed consent has been obtained, including screening failures due to AEs, irrespective of trial intervention. In this trial, AEs during the treatment and follow-up periods will be assessed compared to Day 1.

Medical terminology should be used for AE reporting. Adverse events should be reported as a single unifying diagnosis whenever possible or, in the absence of a unifying diagnosis, as individual signs or symptoms.

Exacerbation or disease progression should be reported as an AE only if there are unusual or severe clinical features that were not present, or experienced earlier, or not expected based on the course of the condition. A reported AE that undergoes worsening in severity or seriousness should be reported as a new AE in the eCRF. However, if worsening of the condition is observed on Day 1 or later, the AE should be reported as a new AE in the eCRF without limiting to worsening in severity or seriousness. If a subject is suspected to have COVID-19 during the trial, the investigator or subinvestigator will confirm the results of an antigen test, etc., and take necessary measures such as a determination on the necessity for discontinuation of the IMP in consideration of the safety of the subjects. A positive result will be reported as an AE in the eCRF.

In addition, the sponsor must be notified immediately by e-mail in principle of any IREs according to the procedure outlined below, in [Section 8.8.3](#). Special attention should be paid to recording hospitalization and concomitant medications.

The AE, start date, end date, seriousness, severity, relationship to trial treatment (IMP causality), action taken with trial treatment, and outcome will be recorded on the source documents and in the eCRF.

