## **9 Statistical Considerations**

### **9.1 Sample Size**

Assuming a withdrawal of approximately 20 subjects during the treatment period, the target number of subjects is set at 120 to ensure that 100 subjects will complete the 1-year treatment to assess the safety of ETC-1002 at 180 mg in long-term administration.

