8.3 Subgroup Analyses

Subgroup analyses will be performed by the following items for the percent change in LDL-C (direct method) from baseline at Weeks 24 and 52. Statin intensity categories and types are shown in [Appendix 6](#). In the data for each statin type, subjects who use multiple medications will be excluded from the summarization.

- Statin response (inadequate response to statins/difficulties in treatment with statins)
- Sex (Male, Female)
- Familial hypercholesterolemia (Yes, No)
- Diabetes mellitus (Yes, No)
- Age (<65 years, ≥65 years and <75 years, ≥75 years)
- Statin use (Yes, No)
- BMI (<25 kg/m², ≥25 kg/m² and <30 kg/m², ≥30 kg/m²)
- eGFR (<60 mL/min/1.73 m², ≥60 mL/min/1.73 m² and <90 mL/min/1.73 m², ≥90 mL/min/1.73 m²)
- LDL-C at baseline (<100 mg/dL, ≥100 mg/dL and <120 mg/dL, ≥120 mg/dL and <140 mg/dL, ≥140 mg/dL)
- Statin intensity (Low-intensity statins, High-intensity statins, No statins)
- Statin type (atorvastatin calcium trihydrate, fluvastatin sodium, pitavastatin calcium, pravastatin sodium, rosuvastatin calcium, simvastatin, no statins)

9 Safety Analyses

For the safety analysis set, the summarization will be performed by rollover, newly enrolled, and overall subjects. Baseline is defined as the last data before the start of IMP administration. The analysis visits will be Weeks 4, 8, 12, 16, 20, 24, 28, 32, 36, 40, 44, 48, and 52, unless otherwise specified. The same analysis will be performed for each statin response (inadequate response to statins/difficulties in treatment with statins). Summarization at the Last Visit will also be performed in addition to summarization at each time point.

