9.1 Extent of Exposure

Descriptive statistics will be calculated for the duration of IMP treatment in the treatment period (Date of final IMP administration – Date of initial IMP administration + 1) and for the total number of days of IMP administration (total number of days taking the IMP in the treatment period). For the duration of IMP treatment, frequency distributions of categorized durations (days) (1-84, 85-168, 169-252, 253-336, and ≥ 337) will be calculated by rollover, newly enrolled, and overall subjects, along with the descriptive statistics.

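### For rollovers already on ETC-1002, safety is measured from an on-drug Day 1; no table separates them, so the rollover column is hard to read and the overall column is diluted for early effects

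*Protocol*

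**What the plan says.** Protocol 4.1 admits subjects who completed treatment in 346-102-00002, because "their enrollment allows assessments of the occurrence of AEs over a longer period". The Protocol 1.2 schema sends them directly into open-label treatment after 12 double-blind weeks. Footnote b of the schedule in 1.3 takes their Day 1 values from the confirmatory trial's Week 12 tests.

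The reference point is the same for everyone:

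- **Baseline.** Protocol 9.4.2 and SAP 9 use the last value before the investigational product starts in this trial.
- **Adverse events.** Protocol 8.8.2 states that "AEs during the treatment and follow-up periods will be assessed compared to Day 1". Under Protocol 8.8.1, an event from the confirmatory trial that "continues without recovery/resolution but does not worsen, the event will not be included as an AE in this trial". An event that worsens after dosing starts is counted.
- **Exposure and onset.** SAP 9.1 says "Descriptive statistics will be calculated for the duration of IMP treatment in the treatment period". The onset bands in SAP 9.2 start at days 1-14, with no rule for earlier exposure.

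On presentation, SAP 9 says: "For the safety analysis set, the summarization will be performed by rollover, newly enrolled, and overall subjects". The tables are repeated by statin response. None splits rollovers by the treatment they received in 346-102-00002.

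Newly enrolled subjects are excluded under criterion 18 in Protocol 5.2.2 if they are "Patients who took the IMP in Trial 346-102-00001 or patients who have used ETC-1002 in the past". The stated rationale is "10) to 11), 14), 18) These criteria are set to appropriately evaluate the safety of ETC-1002".

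**The concern.** Safety is the primary objective. A rollover who has taken ETC-1002 for 12 weeks enters with any early effect already in the baseline. The same subject has also been selected: Protocol 5.2.1 requires completion of the 12 weeks without meeting the discontinuation criteria. Events that began and persisted unchanged, or that resolved before Day 1 and did not recur, do not appear here.

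The protocol bars other prior users so that safety can be judged properly, and it admits rollovers in order to follow adverse events for longer. No planned table follows them from first dose or adds the two exposure periods together.

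Two displays suffer. The rollover column may combine two groups with different baselines and cannot be read as either. The overall column averages first-time users with subjects whose early effects lie outside the window. Neither document says which of the three columns answers the primary objective, and SAP 6 states that there are no primary or secondary outcome variables.

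**Working it through.** **The plan's own figure.** Protocol 9.1: "Assuming a withdrawal of approximately 20 subjects during the treatment period, the target number of subjects is set at 120". 120 - 20 = 100 completers, and 100 / (1 - 20/120) = 120. This reproduces and is not affected. It refers to the whole trial; no minimum is set for newly enrolled subjects.

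**Onset and exposure.** Twelve weeks is 84 days. For a subject already on drug, onset days 1-14 here are exposure days 84 + 1 = 85 to 84 + 14 = 98. A completer's cumulative exposure is 12 + 52 = 64 weeks, but is reported as 52.

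**Adverse event incidence.** Let p be the rate of events starting in the first 12 weeks of exposure, f the share of treated subjects with prior ETC-1002, and s the share of those subjects' early events that never enter this trial's counts (not worsened, not recurring). Then

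overall incidence = p × (1 - f × s).

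For illustration, p = 11/141 = 7.8%, the phase 2 rate of hyperuricaemia-related events (Protocol 4.2). The values of f and s are assumptions.

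**Change from baseline.** Protocol 2.3 reports that mean uric acid rose within the first month and then held steady. If such a mean has fully plateaued by Week 12, prior users contribute about zero further change, and the overall mean change is the true change × (1 - f).

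| Rollovers of 120 | Share with prior ETC-1002 | f | Overall, s = 0.5 | Overall, s = 1 | Mean change retained |
|---|---|---|---|---|---|
| 0 | - | 0 | 7.8% | 7.8% | 100% |
| 30 | 1/2 | 0.125 | 7.3% | 6.8% | 87.5% |
| 60 | 1/2 | 0.25 | 6.8% | 5.9% | 75% |
| 60 | 2/3 | 0.333 | 6.5% | 5.2% | 67% |
| 90 | 2/3 | 0.5 | 5.9% | 3.9% | 50% |

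For the third row: 7.8% × (1 - 0.25 × 0.5) = 6.8%, and 7.8% × (1 - 0.25) = 5.9%.

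In the rollover column alone, with half on prior drug, the same rate would read 7.8% × (1 - 0.5 × 0.5) = 5.9% or 7.8% × (1 - 0.5) = 3.9%. The newly enrolled column stays at 7.8% throughout.

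**The 5% tables.** SAP 9.2 selects common events by incidence among all subjects. At f = 0.25, an early event needs a first-exposure rate of 5% / 0.875 = 5.7% (s = 0.5) or 5% / 0.75 = 6.7% (s = 1) to be listed. The full tables still show it.

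**What the newly enrolled column costs in precision.** With 60 newly enrolled subjects and no event seen, the one-sided 95% upper bound is 1 - 0.05^(1/60) = 4.9%. Adding 30 rollovers without prior ETC-1002 gives 90 first-time users and 1 - 0.05^(1/90) = 3.3%.

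**What depends on baseline.** Affected: mean changes, laboratory shift tables, QTcF change counts, the hematocrit criterion (SAP Appendix 2), and the vital-sign, weight and ECG criteria with a change component (Appendices 1 and 3). Not affected: most Appendix 2 limits (including uric acid, AST/ALT, CK, creatinine and hemoglobin), the Hy's law rule, and the QTcF level counts.

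**The case against.** The best defence is that a clean answer is already planned. Every safety summary has its own newly enrolled column, those subjects must be ETC-1002-naive, and their Day 1 is off drug. This stands. A reader might infer that the primary safety answer is understated; the documents do not support that, because neither names the overall column as the answer.

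Second, the carry-over rule is narrow and avoids counting in this trial events that arose in another. Worsening counts, and Protocol 8.8.2 makes any worsening from Day 1 a new event whether or not severity or seriousness changes. Current conditions at consent are recorded and medical history is listed. This also stands, although such records do not put persisting events into any incidence table.

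Third, a reader might set s = 1, assume 20, 40 or 60 prior users, and report a 17%, 33% or 50% understatement. Those figures merely restate the assumed share of 120, and they require that prior users have no such event in 52 weeks. The 7.8% itself pools the 60, 120 and 180 mg groups (47 + 46 + 48 = 141).

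Fourth, a reader might expect prior users to show no uric acid rise at all. Protocol 2.3 describes pooled means, not individuals, and actual values are tabulated too.

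What the defence does not answer is that the rollover column cannot be interpreted, that the stated reason for enrolling rollovers is served by no table, and that no column is designated for early effects.

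**Conclusion.** The point holds as a reporting gap in a descriptive, single-arm trial with no test or decision threshold. It is worth fixing, but it does not invalidate the plan. The direction is supported for the overall and rollover columns: toward no effect for early-onset events and for change-from-baseline displays. The size cannot be stated from the documents. The illustration of 7.8% reading as 6.8% to 5.9% overall rests on 60 rollovers, half with prior ETC-1002, and half to all of their early events going uncounted. With no prior users the dilution is zero. The documents call the confirmatory trial double-blind but do not give its arms, so the proportion of rollovers without prior ETC-1002 is also an assumption.

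**What to change.** In SAP 9, keep the planned columns and the Day 1 baseline, and add:

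1. A split of the rollover column by treatment received in 346-102-00002, after that trial is unblinded. Protocol 8.1 already foresees the unblinding.
2. A first-exposure group (newly enrolled plus rollovers without prior ETC-1002), named as the reference display for early-onset adverse events, onset time and laboratory change.
3. For rollovers with prior ETC-1002, a supplementary analysis of adverse events, onset and cumulative exposure from the first ETC-1002 dose, using the laboratory baseline before that dose. Extend the exposure bins beyond 52 weeks; the top bin in SAP 9.1 is now open-ended from day 337.
4. A listing of adverse events ongoing at Day 1.

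The cost is a merge of the confirmatory trial's treatment codes and its adverse event, laboratory and exposure data, plus extra tables. Trial conduct does not change. Item 3 uses a baseline and event window that differ from Protocol 9.4.2 and 8.8.1, so label it supplementary. State alongside it that prior users remain a selected group of 12-week completers, which the added tables do not correct.

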### 8.8.2 Eliciting and Reporting Adverse Events

The investigator or subinvestigator will regularly assess the subjects for the occurrence of AEs. To avoid bias in eliciting AEs, subjects should be asked the nonleading question: “How have you felt since your last visit?” All AEs (serious and nonserious) reported by the subject must be recorded on the source documents and eCRF provided by the sponsor. Adverse event collection will begin after a subject signs the ICF and will continue until the end of the follow-up period. All AEs must be recorded in the eCRF after subject informed consent has been obtained, including screening failures due to AEs, irrespective of trial intervention. In this trial, AEs during the treatment and follow-up periods will be assessed compared to Day 1.

Medical terminology should be used for AE reporting. Adverse events should be reported as a single unifying diagnosis whenever possible or, in the absence of a unifying diagnosis, as individual signs or symptoms.

Exacerbation or disease progression should be reported as an AE only if there are unusual or severe clinical features that were not present, or experienced earlier, or not expected based on the course of the condition. A reported AE that undergoes worsening in severity or seriousness should be reported as a new AE in the eCRF. However, if worsening of the condition is observed on Day 1 or later, the AE should be reported as a new AE in the eCRF without limiting to worsening in severity or seriousness. If a subject is suspected to have COVID-19 during the trial, the investigator or subinvestigator will confirm the results of an antigen test, etc., and take necessary measures such as a determination on the necessity for discontinuation of the IMP in consideration of the safety of the subjects. A positive result will be reported as an AE in the eCRF.

In addition, the sponsor must be notified immediately by e-mail in principle of any IREs according to the procedure outlined below, in [Section 8.8.3](#). Special attention should be paid to recording hospitalization and concomitant medications.

The AE, start date, end date, seriousness, severity, relationship to trial treatment (IMP causality), action taken with trial treatment, and outcome will be recorded on the source documents and in the eCRF.

